## SYNOPSIS

|  |  |
|--|--|
| Study Title: Evaluation of Hyperpolarized  Xe MRI as Compared to  Xe Scintigraphy for the Assessment of Pulmonary Function in Patients being Evaluated for Possible Lung Resection Surgery  |  |
| Name of Finished Product:
Hyperpolarized Xenon (  Xe) Gas in BRANDNAME Device  | Name of Active Ingredient:
 Xe Gas |
| Study Number: POL-Xe-001  | Study Phase: 3                                      |
| Clinical Sites: At least 2 study sites in the United States   |  |
| Primary Objective:
The primary objective of this study is to demonstrate the equivalence of hyperpolarized  Xe MRI as compared to  Xe scintigraphy for the evaluation of pulmonary function.   |  |
| Secondary Objectives:
The secondary objectives of this study are to: 

• Assess the safety and tolerability of hyperpolarized Xe gas;

• Evaluate regional ventilation defects in each of the 6 zones, and

• Demonstrate the equivalence of post-operative forced expiratory volume in 1 second (FEV1) values predicted using hyperpolarized Xe as compared to Xe scintigraphy.

   |  |
| Study Design:
This is a multicenter, randomized, open-label, cross-over Phase 3 study evaluating hyperpolarized  Xe MRI as compared to  Xe scintigraphy for the evaluation of pulmonary function. This study is comprised of 4 periods: 

• Screening: Subjects will be screened for study participation based on inclusion and exclusion criteria. Informed consent will be obtained.

• Imaging: Subjects will undergo hyperpolarized Xe MRI and Xe scintigraphy. During the MRI session, one or more conventional proton MRI scans will also be collected to confirm lung anatomical features. Both Xe scintigraphy and hyperpolarized Xe MRI will be quantified using commercially available software. Images will be interpreted by central readers who are blinded to the subject's medical history and all study assessments. Information related to any AEs will be collected during this period.

• Follow-up: Subjects will be contacted by phone on the day after (+3 days) the completion of all imaging to collect information on any AEs.

• Post-op Follow-up: If the subject has lung surgery, approximately 3 months after surgery the subject will come in for a post-operative FEV1 measurement (spirometry).

 All randomized subjects will be divided between 2 treatment orders in a 1:1 ratio. |  |
| Study Population:
Inclusion Criteria:
Subjects will be eligible for participation in the study only if they meet ALL of the following criteria: 

1. Male or female subjects ≥18 years of age.

2. Subject is being evaluated for possible lung resection (e.g., segmentectomy, lobectomy, or pneumonectomy).

3. Able to undergo MRI imaging and able to fit in the MRI coil.

4. Willing and able to comply with all study procedures.

5. Must understand and voluntarily sign an informed consent form (ICF) prior to any study-specific assessments or procedures.

 Exclusion Criteria:
Subjects will not be eligible for participation in the study if they meet ANY of the following criteria: 

1. Baseline blood oxygen saturation (SpO2) <90% at rest. For patients requiring routine supplemental oxygen, SpO2 measurements should be taken with the patient's normal oxygen supplementation.

  |  |

2. Female subjects of childbearing potential with a positive serum pregnancy test at screening, or who are not taking (or not willing to take) acceptable birth control measures through the Follow-up Period. Adequate birth control methods include with a monogamous partner who was sterilized more than 6 months prior to screening, or measures with a Pearl index of  $<1$  used consistently and correctly (including intrauterine devices, or implantable, injectable, oral, or transdermal contraceptives). Women are not considered to be of childbearing potential if they meet at least 1 of the following 2 criteria as documented by the Investigator:
  - They have had a hysterectomy, bilateral salpingectomy, or bilateral oophorectomy at a minimum of 1 menstrual cycle prior to signing the ICF; or
  - They are post-menopausal: for women  $\geq 55$  years of age, defined as  $\geq 1$  year since their last menstrual period, or for women  $< 55$  years of age, defined as  $\geq 1$  year since their last menstrual period and have a follicle-stimulating hormone (FSH) level in the laboratory's normal range for post-menopausal phase.
3. Women who are lactating and insist on breast feeding.
4. Subjects who have received any other investigational therapy within 4 weeks prior to Screening.
5. Subjects who require anesthesia or heavy sedation to undergo MRI testing. Mild sedation could be acceptable (i.e. a low dose oral acting anxiolytic medication such as alprazolam) as long as, in the opinion of the investigator, the subject meets Inclusion Criteria #4 and #5.

**Planned Number of Subjects:**

Completed: 32 subjects having both a  $^{129}\text{Xe}$  MRI and  $^{133}\text{Xe}$  scintigraphy image.

Subjects who discontinue will be replaced in order to achieve the targeted number of completers.

**Test Product, Dose, and Mode of Administration:**

The test product is hyperpolarized  $^{129}\text{Xe}$  gas and will consist of a volume of hyperpolarized  $^{129}\text{Xe}$  inflated with ultra-high purity nitrogen gas to a final volume of 1 L. Subjects will be required to inhale the 1 L of gas mixture and hold their breath for a maximum of 15 seconds (generally 10-15 seconds, based on the length of the scan) while the MRI is acquired.

During the MRI session, one or more conventional proton MRI scans will be collected to confirm lung anatomical features. Subjects will be required to take a full inhalation breath of room air and hold their breath for a maximum of 15 seconds while the MRI is acquired.

Up to 750 mL hyperpolarized  $^{129}\text{Xe}$  gas will be administered to the subject while in the MRI scanner. If the resulting scan is determined or thought to be inadequate, then a calibration dose (approximately 100 mL hyperpolarized  $^{129}\text{Xe}$  gas) will be administered followed by another full ( $\leq 750$  mL) dose. The calibration dose is administered to allow for adjustments of MRI parameters, as needed, to ensure best image quality.

**Reference Product, Dose, and Mode of Administration:**

The reference standard is the anterior and posterior wash-in views of a  $^{133}\text{Xe}$  scintigraphy scan.  $^{133}\text{Xe}$  is administered by inhalation from a closed respirator system or spirometer in accordance with the Package Insert.

Subjects will be exposed to  $^{133}\text{Xe}$  gas for 3-4 minutes, as tolerated.

**Duration of Treatment:**

Depending on the number of doses required to obtain adequate images, subjects will be exposed to hyperpolarized  $^{129}\text{Xe}$  for 15-45 seconds.

Subjects will be exposed to  $^{129}\text{Xe}$  gas for approximately 15 seconds per scan.

**Duration of Subject Study Participation:**

Subjects are expected to participate in this study for a maximum of 15 days unless the subject undergoes resection surgery. For the sub-set of subjects undergoing surgery, the maximum duration for study participation is 4 months.

**Efficacy Assessments:**

Primary Efficacy Endpoints:

The primary endpoint is the scan predicted post-operative FEV1. The scans will be quantified using commercially available software to report the fraction of activity arising from 6 zones. This will be used to predict post-operative FEV1 by multiplying the percentage of function remaining in the non-operated zones by pre-operative FEV1.

Secondary Efficacy Endpoints:

The secondary efficacy endpoints include the post-operative FEV1 value (spirometry) and the percentage function contributed by each of the individual 6 lung zones.

**Safety Endpoints:**

Safety and tolerability will be assessed based on the incidence and severity of treatment emergent adverse events (AEs) and serious adverse events (SAEs). Additionally, subjects will be monitored before, during, and after each dose to monitor for changes in vital signs.

**Statistical Methods:**

*Sample Size Determination:*

The sample size required to demonstrate equivalence is driven by 2 factors: 1) the intra-subject variability of the difference between the predicted post-operative FEV1 from the 2 methods, and 2) the pre-specified equivalence margin. From prior literature, the intra-subject variability for  $^{133}\text{Xe}$  scintigraphy leads to an estimated variability in predicted post-operative FEV1 of 0.21 L/sec. Similarly, prior studies have suggested that the equivalence margin between the 2 imaging techniques currently used for resection planning is 0.3 L/sec. Using these assumptions, and based on the use of a two-sided test at the  $\alpha=0.05$  level of significance, a sample size of 15 subjects is required for 90% power. However, given limited literature on  $^{133}\text{Xe}$  variability, we account for the possibility that it could be higher. If true variability is 0.32 L/sec, then a sample size of 32 subjects will provide 90% power to establish equivalence.

*Primary Analysis:*

The primary analysis for this study will be to test the mean difference in predicted post-operative FEV1 (measured in L/sec) values as measured using hyperpolarized  $^{129}\text{Xe}$  gas MRI relative to  $^{133}\text{Xe}$  scintigraphy (reference standard). The primary analysis will be conducted by estimating the 95% confidence interval (CI) for the mean difference in predicted FEV1 from the 2 methods. The scans will be quantified using commercially available software to report the fraction of activity arising from 6 zones. This will be used to predict post-operative FEV1 by multiplying the percentage of function remaining in the non-operated zones by pre-operative FEV1. The CI will be constructed assuming that the within-subject difference between methods is normally distributed. If the 95% CI for the mean difference is contained within the interval (-0.30, +0.30 L/sec), equivalence will have been demonstrated.

*Secondary Analysis:*

The post-operative secondary analysis for this study will be to test the mean difference in predicted post-operative FEV1 (measured in L/sec) values as measured using hyperpolarized  $^{129}\text{Xe}$  gas MRI and  $^{133}\text{Xe}$  scintigraphy (reference standard) relative to the final post-operative FEV1 value (spirometry). The secondary equivalence analysis will be conducted using the same methodology and same equivalence margin as specified for the primary analysis.

The 6-zone secondary analysis for this study will be to evaluate the individual percentage function assessments from each of the 6 zone analyses from both the  $^{129}\text{Xe}$  and the  $^{133}\text{Xe}$  ventilation images. The equivalence margin will be 5 percentage points. Thus, for each of the six zones, equivalence will have been demonstrated if the 95% CI for the mean difference is contained within the interval (-5%, +5%).

*Safety Analysis:*

All AEs will be summarized by system organ class (SOC), preferred term, severity and relationship to study drug. AEs leading to death or to discontinuation from study drug as well as the SAEs will also be tabulated. In the by-subject summary, a subject having the same event more than once will be counted only once and by greatest severity.

Vital sign measurements, including change from baseline, will be summarized.  
All safety analyses will be performed on the Safety population.

**Interim Analyses:**

No formal interim analyses are planned for this study.

## LIST OF ABBREVIATIONS AND TERMS DEFINITIONS

| Abbreviation      | Definition  |
|-------------------|---|
|  Xe | non-radioactive isotope of xenon (hyperpolarized  Xe is the drug product) |
| ADR               | adverse drug reaction   |
| AE                | adverse event   |
| BP                | blood pressure  |
| CFR               | Code of Federal Regulations   |
| CI                | confidence interval   |
| COPD              | chronic obstructive pulmonary disease   |
| CRO               | Contract Research Organization  |
| eCRF              | electronic case report form   |
| FEV1              | forced expiratory volume in 1 second  |
| FSH               | follicle stimulating hormone  |
| GCP               | Good Clinical Practice  |
| He                | helium  |
| HR                | heart rate  |
| IB                | Investigator's Brochure   |
| ICF               | informed consent form   |
| ICH               | International Conference on Harmonization   |
| IND               | Investigational New Drug  |
| IRB               | Institutional Review Board  |
| ITT               | intent-to-treat   |

|                   |   |
|-------------------|---|
| Lobectomy         | Refers to the removal of a lobe (or lobes).   |
| MedDRA            | Medical Dictionary for Regulatory Activities  |
| MRI               | Magnetic Resonance Imaging  |
| N 2    | nitrogen  |
| Pneumonectomy     | Refers to the removal of an entire lung.  |
| Q                 | perfusion scan  |
| RBC               | red blood cells   |
| Resection         | For this study, the definition of resection surgery includes segmentectomies, lobectomies, and pneumonectomies. |
| SAE               | serious adverse event   |
| Segmentectomy     | Refers to the removal of an area of the lung that is smaller than a lobe  |
| SNR               | signal-to-noise ratio   |
| SOC               | system organ class  |
| SpO 2  | blood oxygen saturation   |
| $^{99m}\text{Tc}$ | Metastable nuclear isomer of technetium-99 isotope  |
| TEAE              | treatment-emergent adverse event  |
| US                | United States   |
| V                 | ventilation scan  |
| WHO               | World Health Organization   |
| Xe                | xenon   |

## 1. INTRODUCTION

Polarean, Inc. (Polarean, the Sponsor) has developed a drug/device combination to administer hyperpolarized  $^{129}\text{Xe}$  as a diagnostic agent used in conjunction with magnetic resonance imaging (MRI) for the evaluation of pulmonary function and for imaging the lungs. The proposed patient population includes patients requiring imaging evaluation of pulmonary function prior to a variety of lung surgeries. Today, these pre-operative evaluations employ nuclear scintigraphy methods using  $^{133}\text{Xe}$  ventilation and/or Technetium ( $^{99\text{m}}\text{Tc}$ ) perfusion (the so called ventilation/perfusion [V/Q] scan). The primary objective for this study is to demonstrate the equivalence of hyperpolarized  $^{129}\text{Xe}$  MRI as compared to  $^{133}\text{Xe}$  scintigraphy.

The population referred for such scans includes patients undergoing evaluation for possible lung resection surgery and transplants. In both circumstances, regional pulmonary function information is used for making surgical decisions. For this study, the population will include patients being evaluated for possible lung resection surgery. The definition of lung resection surgery includes segmentectomies, lobectomies, and pneumonectomies. Segmentectomies refer to the removal of an area of the lung that is smaller than a lobe. A lobectomy is the removal of a lobe (or lobes), whereas a pneumonectomy is the removal of an entire lung ([BMC website](#)).

### 1.1. Hyperpolarized $^{129}\text{Xe}$ in BRANDNAME Device

This device is comprised of 3 different components. Together, these components hyperpolarize, measure the hyperpolarization of  $^{129}\text{Xe}$  gas, and permit administration to the patient. Inhalation of the hyperpolarized inert gas allows for clear imaging of its distribution within the lungs when using any multi-nuclear capable MRI scanner. The 3 components are the Hyperpolarizer, the Polarization Measurement Station, and the Gas Delivery Bag (refer to [Figure 2](#)).

The drug product is hyperpolarized  $^{129}\text{Xe}$ . It is created by passing a gas mixture of xenon (Xe), helium (He), and nitrogen ( $\text{N}_2$ ) through the Hyperpolarizer. Once the Xe is hyperpolarized, it is collected in a Gas Delivery Bag and filled to volume (1 L) with with inert  $\text{N}_2$  buffer gas. Within 5 minutes prior to administration to the subject, the degree of hyperpolarization is measured with the Polarization Measurement Station (refer to [Section 6.9.1](#)). The standard volume (dose) of hyperpolarized  $^{129}\text{Xe}$  is  $\leq 750$  mL administered (via inhalation) to the subject while in the MRI (refer to [Section 5.2.1](#)).

### 1.2. Mechanism of Action

Mechanistically, hyperpolarized  $^{129}\text{Xe}$  is metabolized in order to achieve its primary purpose. After imaging, the hyperpolarized  $^{129}\text{Xe}$  is exhaled from the body during normal respiration.

### 1.3. Pharmacokinetics

Hyperpolarized  $^{129}\text{Xe}$  is chemically and biologically identical to non-polarized Xe, which is a “perfusion-limited” gas and therefore not subject to membrane diffusion ([Roughton and Forster, 1957](#)). It can therefore be assumed that the Xe concentration in the venous capillary blood equilibrates instantaneously with the Xe concentration in the alveoli according to its Ostwald solubility. Data have demonstrated that Xe concentration is diminished by more than  $1000\times$  prior to achieving 40 breaths. Normal humans breathe at a rate of 12-20 breaths per minute ([Guyton and Hall, 2006](#)), therefore the 40-breath mark would be reached at 2-3 minutes. Because blood and airspaces remain in close equilibrium, it is anticipated that the Xe concentration in blood will follow an identical decay curve; however, it will start at a lower concentration. As only one breath of Xe is used for MRI imaging (rather than breathing to equilibrium), it is anticipated that Xe exhalation in patients with lung disease will be similar to that of healthy volunteers.

Detailed information on the pharmacokinetics of Xe and  $^{129}\text{Xe}$  is provided in the [Investigator’s Brochure \(IB\)](#).

### 1.4. Nonclinical Evaluations

A single-dose toxicity study was completed in Beagle dogs under IND 075,010 by GE Healthcare (Report No. FY01-015). Results from clinical observations, ophthalmologic examinations, body weights, food consumption, clinical pathology, and pulmonary function all indicated that no biologically significant adverse effects of exposure were observed. The beagle dogs were observed during exposure as well as for 14 days after exposure to depolarized  $^{129}\text{Xe}$ .

Expanded, single-dose toxicity studies in rats and dogs have been conducted with Xe gas enriched with  $^{129}\text{Xe}$  to 50% v/v. No signs of toxicity, beyond the known physiological effects of Xe gas as an asphyxiant and anesthetic, were observed in these studies.

Literature supports that  $^{129}\text{Xe}$  gas does not affect the hepatic and renal systems ([Reinelt et al., 2002](#)), is non-reactive, and is excreted quickly via the lung. Toxicity data from repeat-dose reproductive and developmental ([Lane et al., 1980](#); [Burov et al., 2002a](#); [Burov et al., 2002b](#)), and immunotoxicological ([Burov et al., 2002c](#); [Horn et al., 2001](#); [de Rossi et al., 2001](#); [de Rossi et al., 2002](#); [de Rossi et al., 2004](#)) studies show no evidence that inhalation of Xe gas causes any specific toxic effects.

Detailed information on the nonclinical evaluation of Xe and  $^{129}\text{Xe}$  is provided in the [IB](#).

## 1.5. Clinical Experience

To date, the clinical development program for hyperpolarized  $^{129}\text{Xe}$  gas in the BRANDNAME device is comprised of 1 Phase 1 study (GE-141-001) and data reported in the literature. The Phase 1, single-site, open-label, non-randomized study was conducted by GE Healthcare and is reported in the literature by [Cleveland et al., 2010](#); [Driehuys et al., 2012](#); [Kaushik et al., 2011](#); [He et al., 2014a](#); and [Virgincar et al., 2013](#). Additional literature support comes from [Kirby et al., 2013](#); [He et al., 2014b](#); [Svenningsen et al., 2013](#); [He et al., 2015](#); and [Stewart et al., 2015](#).

Across these studies, a total of 55 healthy volunteers, 20 patients with chronic obstructive pulmonary disease (COPD, 10 of which had radiographic evidence of emphysema), 27 patients with asthma, and 1 current smoker (healthy) have been administered 1 or more hyperpolarized  $^{129}\text{Xe}$  scan (total exposed to 1 or more doses = 103). No treatment-emergent adverse events (TEAEs) or laboratory changes were reported.

Detailed information on the clinical evaluation of Xe and  $^{129}\text{Xe}$  is provided in the [IB](#).

## 1.6. Rationale for Study

The investigational product is a non-radioactive, 3-dimensional MRI procedure that will allow physicians to clearly and accurately visualize the spatial distribution of a subject's regional pulmonary function. This study was designed to evaluate the ability of hyperpolarized  $^{129}\text{Xe}$  to provide clear images as compared to  $^{133}\text{Xe}$  scintigraphy for the evaluation of pulmonary function.

## 2. STUDY OBJECTIVES

### 2.1. Primary Objective

The primary objective of this study is to demonstrate the equivalence of hyperpolarized  $^{129}\text{Xe}$  MRI as compared to  $^{133}\text{Xe}$  scintigraphy for the evaluation of pulmonary function.

### 2.2. Secondary Objectives

The secondary objectives of this study are to:

- Assess the safety and tolerability of hyperpolarized  $^{129}\text{Xe}$  gas;
- Evaluate regional ventilation defects in each of the 6 zones, and
- Demonstrate the equivalence of post-operative forced expiratory volume in 1 second (FEV1) values predicted using hyperpolarized  $^{129}\text{Xe}$  as compared to  $^{133}\text{Xe}$  scintigraphy.

### 3. INVESTIGATIONAL PLAN

[figure not shown]
#### 3.1. Overall Study Design and Plan

This is a multicenter, randomized, open-label, cross-over Phase 3 study evaluating hyperpolarized  $^{129}\text{Xe}$  gas MRI as compared to  $^{133}\text{Xe}$  scintigraphy for the evaluation of pulmonary function. This study will enroll male and female subjects being evaluated for possible lung resection surgery (i.e. segmentectomy, lobectomy, or pneumonectomy).

The planned enrollment is 32 subjects who have completed the study. Completed subjects will have both a  $^{129}\text{Xe}$  MRI and  $^{133}\text{Xe}$  scintigraphy image. Subjects who discontinue will be replaced in order to achieve the targeted number of completers.

Unless required for safety reasons, all image review will be performed by central readers who are blinded to the subject's medical history and all study assessments. As is shown in Figure 1, this study is composed of 4 periods. All randomized subjects will be divided between 2 treatment orders in a 1:1 ratio.

**Figure 1 Illustration of Study Design for Protocol POL-Xe-001**

\* Screening and Imaging can occur on the same or different days. However, there should be  $\leq 48$  hours between administration of the study drug and reference standard scans.  
\*\* Can occur up to +3 days after completion of imaging but prior to resection surgery.

The 4 study periods are defined as:

- Screening: Subjects will be screened for study participation based on inclusion and exclusion criteria. Informed consent will be obtained and the investigator's assessment of potential locations of lung resection will be recorded on the electronic case report form (eCRF).
- Imaging: Subjects will undergo hyperpolarized  $^{129}\text{Xe}$  MRI and  $^{133}\text{Xe}$  scintigraphy. Both  $^{133}\text{Xe}$  scintigraphy and hyperpolarized  $^{129}\text{Xe}$  MRI will be quantified using commercially

available software. Images will be interpreted by central readers who are blinded to the subject's medical history and all study assessments. Information related to any AEs will be collected during this period.

- **Imaging Follow-up:** Subjects will be contacted by phone on the day after (+3 days) the completion of all imaging to collect information on any adverse events (AEs).
- **Post-op Follow-up:** If the subject has lung surgery, approximately 3 months after surgery the subject will return for a post-operative FEV1 measurement (spirometry).

Following completion of screening and baseline eligibility assessments, all subjects will receive both a hyperpolarized  $^{129}\text{Xe}$  MRI and  $^{133}\text{Xe}$  scintigraphy. During the MRI session, one or more proton MRI scans will also be collected to confirm lung anatomical features. Subjects will receive standard of care at the discretion of the investigator, including appropriate therapies, unless otherwise specified in this protocol. If a subject undergoes resection surgery, an additional study visit to record post-operative FEV1 levels (spirometry) will be required approximately 3 months after surgery.

Safety will be monitored after the administration of both hyperpolarized  $^{129}\text{Xe}$  and  $^{133}\text{Xe}$  (Day 1) and again on Day 2 during the Imaging Follow-up period.

The Schedule of Assessments is provided in [Appendix 1](#). The study endpoints are provided in [Section 8.4](#).

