## 6. STUDY PROCEDURES

The Schedule of Assessments is provided in [Appendix 1](#). All assessments and treatments are to be performed either at a hospital or in a doctor's office.

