## Appendix 1 Schedule of Events

|   | Screening  | Imaging  | Imaging Follow-up  | Post-Op Follow-up  |
|---|------------------------|----------------------|--------------------------------|--------------------|
| Evaluation  | Day -7 to Day 0        | Day 1                | Day 2                          | 1-2 Months Post-Op |
| Informed Consent                                  | X                      |                      |                                |                    |
| Inclusion/Exclusion Criteria                      | X                      | X                    |                                |                    |
| Demographics and Medical History      | X                      | X                    |                                |                    |
| Physical Exam                                     | X                      |                      |                                |                    |
| Concomitant Medications Review                    | X                      | X                    |                                |                    |
| MRI-suitable Screening                            | X                      |                      |                                |                    |
| Recording of potential resection location on eCRF | X                      |                      |                                |                    |
| Spirometry (FEV1)                     |                        | X                    |                                | X                  |
|  Xe Administration      |                        | X                    |                                |                    |
| Anatomical proton MRI (MRI session only)          |                        | X                    |                                |                    |
|  Xe Administration      |                        | X                    |                                |                    |
| Vital Signs                         | X                      | X                    |                                |                    |
| SpO 2                      | X                      | X                    |                                |                    |

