#### 4.3.2. Visit Windows

There are no visit windows for this study, while time windows are allowable for study assessments as shown in [Appendix 11.1](#). For the statistical analyses, data will be analyzed by their time point of collection.

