##### 4.4.2.2. Post-Operative Analysis

The post-operative secondary analyses for this study will be to compare the final measured post-operative FEV1 value (spirometry) to those predicted by both hyperpolarized  $^{129}\text{Xe}$  MRI and  $^{133}\text{Xe}$  scintigraphy.

The calculation of predicted post-operative FEV1 will be based on pre-operative imaging and the extent of planned lung resection. The scans will be quantified using commercially available software to report the fraction of activity arising from each of 6 lung zones, 3 in each lung. On the eCRF, the surgeon will check the zones that are planned for resection. The predicted post-operative FEV1 will be calculated by multiplying the percentage of function remaining in the non-operated zones by the pre-operative FEV1. For example, assume that the quantified fractions of activity for zone 1 to zone 6 are 15%, 20%, 25%, 10%, 15% and 15%, respectively and the surgeon notes that zone 4 and zone 5 are planned for complete resection. Then, the predicted post-operative FEV1 = pre-operative FEV1 \*  $\{(15\%+20\%+25\%) + (15\%)\}$ .

For each of these two comparisons, the null hypothesis that the mean difference is equal to zero, will be tested using the one-sample t test. The two-sided 95% CI for the mean difference will also be reported. A third comparison will be to test the null hypothesis that the mean difference between predicted post-operative FEV1 (measured in L) predicted by hyperpolarized  $^{129}\text{Xe}$  MRI and  $^{133}\text{Xe}$  scintigraphy is equal to zero. This analysis will also be conducted using the one-sample t test and the two-sided 95% CI for the mean difference will be reported.

This analysis will use the Post-operative Analysis Set. Because the final post-operative FEV1 value will be obtained approximately 3 months after surgery, this post-operative secondary analysis will be performed about 3 months after the other planned statistical analyses.

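### The text puts post-operative spirometry at about 3 months but both Schedules of Events put it at 1-2 months, so two secondary comparisons could pool FEV1 values taken at different times (minor)

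*Protocol*

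**What the plan says.** Six narrative statements give a time for the post-operative FEV1 visit, and all six say about 3 months.

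- Protocol synopsis, Study Design: "approximately 3 months after surgery the subject will come in for a post-operative FEV1 measurement (spirometry". SAP section 1.2 has the same sentence.
- Protocol section 3.1, definition of the fourth study period: "approximately 3 months after surgery the subject will return for a post-operative FEV1 measurement (spirometry".
- Protocol section 3.1, after the period definitions: "an additional study visit to record post-operative FEV1 levels (spirometry) will be required approximately 3 months after surgery". SAP section 1.2 repeats this too.
- SAP section 4.4.2.2: "Because the final post-operative FEV1 value will be obtained approximately 3 months after surgery", from which it follows that "this post-operative secondary analysis will be performed about 3 months after the other planned statistical analyses".

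The Schedule of Events in Protocol Appendix 1 heads the Post-Op Follow-up column "1-2 Months Post-Op", and the spirometry row is marked in that column. SAP section 11.1 carries the same heading and the same mark.

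Both documents send their users to these tables. Protocol section 6 opens with "The Schedule of Assessments is provided in" Appendix 1, and section 3.1 makes the same reference. SAP section 4.3.2 states "There are no visit windows for this study, while time windows are allowable for study assessments as shown in" Appendix 11.1, and adds that data are analysed by the time at which they were collected.

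**The concern.** A site that works from the schedule would call the subject back at 1 to 2 months. A site that works from the text would do so at about 3 months. The plan cannot be followed both ways.

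Measured FEV1 is the benchmark in two of the three comparisons in SAP section 4.4.2.2: measured against the 129Xe prediction, and measured against the 133Xe prediction. Each mean difference is tested against zero with a one-sample t test and reported with a 95% CI. If FEV1 changes with time since surgery, the time of the visit is part of what the measured value means. Mixed timing would then make those two mean differences harder to interpret. They are also the only planned check of either scan's prediction against a measured outcome.

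**Working it through.** The point rests on the text, so the check sets the statements side by side and then traces where a measured FEV1 value enters the analysis.

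**1. Do the stated times overlap?**

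| Source | Time of post-operative spirometry |
|---|---|
| Protocol synopsis | about 3 months |
| Protocol 3.1 (two statements) | about 3 months |
| SAP 1.2 (two statements) | about 3 months |
| SAP 4.4.2.2 | about 3 months |
| Protocol Appendix 1 | 1-2 months |
| SAP 11.1 | 1-2 months |
| Protocol 6.7 | names the period, gives no time |

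Gap from the upper end of the schedule range: 3 − 2 = 1 month. Gap from the lower end: 3 − 1 = 2 months. There is no overlap unless the word approximately is stretched by a month or more.

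**2. Does anything reconcile them?** The spirometry footnote in both schedules concerns only the measurement before imaging. Protocol section 6.7, the spirometry procedure, gives no time. SAP section 4.3.2 sets no visit window and refers back to the schedule. SAP section 9, which lists changes from the protocol, does not mention the visit time. The conflict does not depend on the amendment log, because Appendix 1 and SAP section 11.1 are themselves current.

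**3. Would the analysis separate early from late values?** No. The Post-operative Analysis Set in SAP section 4.2.1 requires acceptable scans and a post-operative FEV1 value, with no limit on timing. A 1-month value and a 3-month value both qualify and would be averaged together.

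**4. Which results use the measured value?** Write M for measured post-operative FEV1, and P129 and P133 for the two predictions. Suppose a fraction f of subjects is measured early and early measurement changes M by d on average. The mean of M then moves by f × d.

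- Mean of (M − P129) moves by f × d.
- Mean of (M − P133) moves by f × d.
- Mean of (P129 − P133) moves by 0, because M does not enter it.
- The primary endpoint (predicted proportion of remaining function) and the six zone comparisons contain no M, so they move by 0.
- The sample size in SAP section 2 is built on the difference between scans, so it does not change.

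The values affected are therefore those in 2 of the 3 comparisons in SAP section 4.4.2.2, and both move by the same amount.

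**5. How large is f × d?** The documents give neither term. They contain no rate of FEV1 recovery after resection and no statement of how many subjects would be measured at each time. They also give no number of operated subjects and no SD for measured minus predicted FEV1. The effect cannot be put in litres or turned into a p-value.

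**The case against.** The best case against raising this is that the answer is already plain. All six narrative statements agree on about 3 months, one of them makes the visit at that time a requirement, and the SAP's own timetable for the post-operative analysis assumes it. On that view the schedule heading is an uncorrected slip, nothing shows that any site followed it, and only two secondary tests with no equivalence margin or success rule are exposed. Much of this stands, and it is why the point is minor. It does not remove the point. The schedule is the table that sites and analysts are told to use, the same heading appears in both documents, and the spirometry section gives no time that would override it.

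A reader might infer more than the documents support, in four ways.

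- **That mixed timing would make one scan look biased and the other not.** A timing shift moves both mean errors equally. For it to separate the two tests, the predictions must already differ, and the third comparison in SAP section 4.4.2.2 examines that difference directly. Any worked example also needs an assumed shift, number operated and SD.
- **That membership of the post-operative set would change.** A value at either time admits the subject. Membership would change only if subjects were lost between the two times, and the documents give no basis for that.
- **That the 4-month maximum participation settles the matter.** If surgery follows soon after the 15-day phase (15/30.4 ≈ 0.5 month), a 3-month visit ends at about 3.5 months and a 1-2 month visit at about 1.5 to 2.5 months. Both fit under 4 months, and the interval from imaging to surgery is not stated.
- **That sites did measure at different times.** The documents show only that they could have.

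**Conclusion.** The inconsistency is real and lies in the current text of both documents. Its established size is a gap of about 1 to 2 months between the stated visit times. The consequence is possible pooling of FEV1 values taken at different times in two secondary comparisons of measured with predicted FEV1.

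Whether this biases anything depends on two conditions that the documents do not settle: that FEV1 changes between 1 and 3 months after resection, and that some visits followed the schedule rather than the text. The weight of the text favours 3 months as the intended time, but only the sponsor can confirm that. Severity: minor.

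**What to change.** 1. Correct the Post-Op Follow-up heading in Protocol Appendix 1 and SAP section 11.1 to about 3 months, once the sponsor has confirmed that this is the intended time. Protocol section 9.1 requires IRB approval of amendments, so the protocol heading is best corrected at the next amendment, with a clarification to sites as the alternative.
2. Report a descriptive summary of days from surgery to spirometry for the Post-operative Analysis Set. A new heading cannot alter visits already made, and for those this summary shows the actual timing. It needs the surgery date; whether the eCRF records it cannot be checked from the documents.
3. Keep every subject in the Post-operative Analysis Set as SAP section 4.2.1 defines it. No new exclusion for timing is needed.

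A stated window around 3 months and a sensitivity analysis restricted to visits inside it are optional. The cost is one heading in each of two documents and one descriptive summary, plus the approval step if the protocol is amended.
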